We will conduct a grey literature review to identify contextual factors influencing access to home and community health services for the selected states, regions, and healthcare systems included in the PRIM-ER study. We choose to conduct a grey literature review versus a systematic review due to the nature of data we desire to obtain. Information on state and federal licensing, for example, are unlikely to be included in a formal research publication. We will also conduct an environmental scan to complete a census report on the type, amount, and location of home and community health services relative to the location of the healthcare systems of interest. The home and community health services of interest for this study include assisted living, skilled nursing care, adult day care, home health services, naturopathic medicine, chiropractic medicine, acupuncture, and massage therapy. Our search strategy will reflect the recommendations from Paez 2017 to balance search specificity and sensitivity without being overly inclusive to a fault.³¹ We will use a combination of resources for our search, including grey literature databases (OpenGrey, WONDER, SCOPUS, Grey Matters, Grev Literature Report, National Technical Information Service, PsycEXTRA, Web of Science, Zetoc), unpublished clinical trials (Clinical Trials.gov, Cochrane Central Registry of Controlled Trials, World Health Organization International Clinical Trials Platform) conference papers (Conference Papers Index), dissertations, theses, and academic papers (ProQuest Dissertation & Theses Global, WorldCatDissertations) web searches (Google, Google Scholar, Mednar), and healthcare system information collected through PRIM-ER. Data of interest includes applicable laws/regulations, number and type of facilities, distance/location of facilities in relation to healthcare systems, and availability of services both within and external to the healthcare system.

Semi- Structured Qualitative Interviews

We will recruit an emergency medicine physician and nurse champion (one each) from all 18 healthcare systems within the PRIM-ER parent study. This will provide us a diverse population of emergency providers from different geographic locations and healthcare systems. Prior to starting the interviews we will explain the purpose of the interview to the participant, and obtain verbal consent. Interviews will be recorded and transcribed. Confidentiality will be protected by immediately downloading the recording to a secure computer and deleting the recordings once they are transcribed. No identifiable information will be recorded. The interviews pose minimal risk to the participants.

Interviews will be completed and recorded using ZOOM teleconferencing and REDCap survey software. The main subsections of the interview guide will include 1.) Provider demographics and healthcare system characteristics 2.) Provider familiarity and attitudes regarding home and community health services for older adults with serious life-limiting illness, 3.) Barriers and facilitators to home and community health services within and out of their healthcare network, and 4.) Availability of integrative medicine services to support older adults with serious life-limiting illness

For interviews conducted aiming to understand CDS implementation in greater detail, we will be inviting 1 Site PI from each of the 18 healthcare systems within the PRIM-ER parent study. We will follow the same protocol, as outlined above for previous qualitative interviews. Prior to starting the interviews we will explain the purpose of the interview to the participant, and obtain verbal consent. Interviews will be recorded and transcribed. Confidentiality will be protected by immediately downloading the recording to a secure computer and deleting the recordings once they are transcribed. No identifiable information will be recorded. The interviews pose minimal risk to the participants.

Interviews will be completed and recorded using ZOOM teleconferencing and REDCap survey software. The main subsections of the interview guide will include: Reach, Effectiveness and Maintenance. This will help us understand the specific barriers or facilitators to the effectiveness implementation and practical use of the PRIM-ER CDS instrument.

Exploratory Analysis

We will conduct an exploratory analysis to examine if access to home and community health services predicts healthcare utilization in the 6 months after an ED visit at the end of life. We will examine correlations between home and community health access factors and healthcare utilization from the 18 healthcare systems included in the PRIM-ER study using the Senior Care Services Scale (SCSS) developed by Arbaje et al.³² Data from all 18 healthcare systems collected from the Grey Literature Review and Qualitative Interviews will be eligible for this exploratory analysis.

Contextual factors from the Grey Literature Review and the Qualitative Interviews will be used to analyze if access to home and community health services predicts healthcare utilization. Healthcare utilization data will be provided from the PRIM-ER study and will be collected from Medicare claims data to include ED revisits (count), inpatient days (count), home health use (Yes/No), and hospice use (Yes/No) in the 6 months from the index PRIM-ER ED visit. These measures of healthcare utilization are based on the Dartmouth Atlas Decedent Cohort Care Intensity Measures to monitor the quality of end-of-life care in Medicare patients. The SCSS will be adapted to PRIM-ER using contextual factors from the Grey Literature Review and Qualitative Interviews 2. Each healthcare system will be assigned a score based on their access to home and community health services.

B) Inclusion and Exclusion Criteria

Eligible patients will include ED patients 66 years or older with serious, life-limiting illness who visited any of our EDs during the implementation of PRIM-ER. Patients must demonstrate one-year mortality of at least 30 percent (score > 6) according to the Gagne Index, a validated instrument used to measure all cause one-year mortality in community-dwelling older adults, calculated based on their prior 12 months before the index ED visit of Medicare claims. ED patients transferred from a nursing home on the index ED visit will be excluded since prediction of mortality and disposition of such patients differs from community-dwelling adults. Patients currently receiving hospice at the time of the index ED visit will also be excluded since they have already received services.

Qualitative Interviews Contextual Assessment

Participants for the provider interviews will include one emergency medicine physician and one nurse champion from each of the 18 healthcare systems already enrolled within the PRIM-ER. As part of PRIM-ER each site has already identified a provider and nurse champion that the study team will outreach. Inclusion criteria includes: Must be a practicing licensed physician or licensed registered nurse within a department of emergency medicine within a healthcare system included in the PRIM-ER study, must be 18 years or older, must be willing to provide verbal consent.

Qualitative Interviews CDS

Participants for the CDS interviews will include one Site PI from each of the 18 healthcare systems already enrolled within the PRIM-ER study. This is completely voluntary and Site PIs do not have to participate if they do not want to and/or do not have the time. As part of PRIM-ER project, each site has already identified a Site PI that the study team will outreach. Inclusion criteria includes: Must be a practicing licensed physician within a department of emergency medicine within a healthcare system included in the PRIM-ER study, must be 18 years or older, must be willing to provide verbal consent.

C) Number of Subjects

We expect to analyze the Medicare claims of over 57,000 patients with serious illness who have made their index ED visit to any of the 35 EDs.

Qualitative Interviews Contextual Assessment

We will recruit 18 licensed emergency medicine physicians and 18 emergency medicine registered nurses for a total of 36 participants for the provider interviews.

Qualitative Interviews CDS We will recruit a maximum of 18 licensed emergency medicine physicians/Site PIs for the CDS interviews.

D) Recruitment and Informed Consent

Medicare claims of patients 66 years and older with serious, life-limiting illness who made a visit to any of our EDs during the study period will be used to measure outcomes in our patient cohort. We will seek a waiver of Health Insurance Portability and Accountability Act (HIPAA) authorization for ED patients as this study presents no more than minimal risk and cannot be practicably conducted without the waiver given the study's geographic breadth and sheer number of participants (>57,000 eligible patients). Obtaining informed consent for participation and use of Medicare claims from all patients in this study is not feasible and will interfere with the conduct of this study.

Qualitative Interviews

We will recruit our participants for the provider interviews through a combination of word-of-mouth and email invitation through the healthcare systems points of contact established via the PRIM-ER study. After a participant expresses interest in participation, they will be contacted by [name] for Contextual Assessment or Senior Research Project Manager ([name]) or Co-Investigator [name] for CDS interview for an expanded explanation of the study, study procedures, their role as a participant, and potential risks and benefits. It will be clearly disclosed that the interview will occur via ZOOM teleconferencing and be recorded. Once the participant is read all study materials and information and had a chance to have all their questions answered, the recording device will be started, and the provider will be asked to provide verbal consent for participation. All qualitative interviews for this project, will follow the same protocol as outlined here.

E) Data Analysis

a. Dependent variables

ED disposition will be measured on the index ED visit, and will be a dichotomous variable for an acute care admission (Yes/No). Acute care admission will be defined as admission to a non-palliative service, and non-acute care admission will include admission to a palliative care service or unit, discharge to home, observation (without a change to inpatient status), or transfer to inpatient or outpatient hospice.

Healthcare utilization will be measured as ED revisits (count), inpatient days (count), home health use (Yes/No), and hospice use (Yes/No) in the 6 months from the index ED visit. These will be identified through revenue codes in each site's administrative data. We developed these measures of healthcare utilization based on the *Dartmouth Atlas Decedent Cohort Care Intensity Measures* to monitor the quality of end-of-life care in Medicare patients with serious chronic illness. ²⁸⁻³⁰

Survival will be measured in days from the index ED visit to death or 6 months, whichever is sooner.

b. Independent variables

Table 1 outlines the independent variables. Independent variables were previously assessed at the time of site implementation. Healthcare system- and provider-level variables were collected by the project manager and via a provider survey at the level of each participating ED. Patient-level variables will be assessed using the CMS Research Data Assistance Center Master Beneficiary Summary File, Base (A/B/D) Segment. The Project Manager will also document if trainings occurred via in-person or virtually to understand more deeply the implementation of the QI initiative at each site.

Table 1. Independent Variables			
Variable	Coding	Source	
Implementation Period	Weeks from Time 0	Project Manager	
Healthcare system/ED-level variables			
Health System	Allegheny, Bay State, Beaumont, Brigham and Women's, Christiana Care, Henry Ford, [name] Anderson, NYU Langone, Ohio State University, Ochsner, Rutgers, Sinai, UC San Francisco, University of Florida, University of Pennsylvania, University of Utah, Yale New Haven	Project Manager	
ED	1—35	Project Manager	
ED Volume	30,000—49,999 visits, 50,000—69,999 visits, 70,000—89,999 visits, ≥ 90,000 visits	Project Manager	
Ownership	Nonprofit, Government, For Profit	Project Manager	
Emergency medicine residency training site	Yes/No	Project Manager	
Free-standing ED	Yes/No	Project Manager	
Dedicated ED social worker/care manager	Yes/No	Project Manager	
US Region	Northeast, Midwest, Southeast, Southwest, West	Project Manager	
Metropolitan Status+	Yes/No	Project Manager	
Outpatient palliative care	Yes/No	Project Manager	
EHR	Epic, Cerner	Project Manager	
Trauma center	Yes/No	Project Manager	
Patient variables			

Age	Years	Master Beneficiary Summary File, Base Segment
Gender	Female, Male, Other	Master Beneficiary Summary File, Base Segment
Race/Ethnicity	Asian, Black, Hispanic, White, North American Native, Unknown, Other	Master Beneficiary Summary File, Base Segment
Gagne index ²⁴	Count of conditions	Inpatient and outpatient RIF
+Population estimates by MSA are based on estimates of the civilian non-institutionalized population of the US as of July 1, 2013, from the 2013 National Health Interview Survey, National Center for Health Statistics, compiled according to the 2013 Office of Management and Budget definitions of core-based statistical areas. See http://www.census.gov/population/metro/ for more about metropolitan statistical area definitions.		

For the PRIM-ER Contextual Assessment that data analysis will vary per specific component.

Grey Literature Review: Data will be collected and analyzed on the regional, state, and healthcare system level. Data will be coded and collated per topic of interest. A combination of descriptive statistics, narrative description, and thematic coding will be used to summarize and present the data.

Qualitative Interviews: For the qualitative data, the interview transcriptions will undergo verbatim transcription and thematic coding. We will develop deductive codes based on the discussion guide, and inductive codes based on salient topics identified during review and coding of the transcripts. We will compare codes across all of the transcripts during the final analysis phase and condense codes into meaningful categories. We will use ATLAS.ti software to facilitate coding as well as cross-investigator and cross-interview analyses. We will also develop data matrices to highlight prominent themes related to facilitators and barriers to home and community health services. For quantitative analysis, we will use descriptive statistics to summarize the data.

Exploratory Analysis: This exploratory analysis will mirror the healthcare utilization analysis and statistical model described in the PRIM-ER. Each healthcare system index score will be used as an independent variable in our predictive model to determine the relationship between home and community health access factors and healthcare utilization in the 6 months after an ED visit at the end of life.

The healthcare system dependent (Ea.) and independent variables (Eb.) described above for PRIM-ER grant will also be used for the analysis of the PRIM-ER Contextual Assessment.

c. Methods

The analytic plan accounts for the nested structure of the data, assesses normality assumptions of dependent variables, and addresses issues related to missing data, study participation bias, and baseline covariate balance. We address each of these in turn. All analyses will be conducted in R 3.3.2 (R Foundation for Statistical Computing, Vienna).

Prior to conducting the outcome analyses, we will compare patients in each ED cluster with respect to patient, provider, and facility characteristics. We will assess whether any adjustments will need to be made in the final statistical models based on whether the differences are clinically meaningful. To account for nesting in the data structure (patients nested in hospitals), we will use mixed effect multi-level models to estimate effect sizes. We anticipate two sources of variation.

The **primary outcome** is the proportion of eligible patients whose disposition is to an acute care setting (inpatient, non-palliative service). The **secondary outcomes** include healthcare service utilization in the 6 months following the ED visit and survival times following the ED visit. The health utilization outcomes include receipt of ED revisits (count), home health services (yes/no), inpatient days (count), admission to an ICU

(yes/no), and admission to hospice (yes/no). The analysis of the effect of PRIM-ER on ED disposition in the context of a stepped-wedge design will be based on a Generalized Linear Mixed Model (GLMM). In particular, to assess the intervention effect, we will use a generalized linear binomial model with random site level effects. The analysis of site, provider, and patient-level characteristics that are associated with variation in impact of PRIM-ER will be based on extending the models used in the analysis plan for ED disposition, healthcare utilization in 6 months following the ED visit, and survival times to include independent variables related to the characteristics of interest.

5. Risks to Subjects

Any information collected from Emergency Department providers will be utilized solely for QI purposes and not analyzed for research.

The study involves using Medicare claims of patients in our patient cohort that contain identifiable personal health information. The largest risk to ED patients is a breach of confidentiality. This will be managed by ensuring that only qualified study team members have access to patient data; all personal identifiers will be removed after final analysis, and all reporting and/or publication of data based on Medicare claims will be in aggregate form. Study team members will also be approved by ResDAC to access the Medicare claims through the Virtual Research Data Center (VRDC), a virtual research environment allowing researchers to have direct access to approved data files to conduct their analysis within the CMS secure infrastructure. All research personnel who have access to electronic records will undergo extensive training to safeguard against this potential risk to emergency provider, key informant, and patient participants, which will include HIPAA certification and CITI training in biomedical research and social and behavioral research.

For the PRIM-ER Contextual Assessment and CDS quantitative survey or qualitative interviews provider information including demographics and interview responses will be recorded and analyzed. The largest risk to ED providers is a breach of confidentiality. There is no expected risk of physical, mental, professional, or financial harm to study participants.

6. Potential Benefits to Subjects

Future patients with serious illness who present to the ED may benefit from the findings of this study.

7. Protections Against Risk

Medicare claims obtained from CMS will be stored in the VRDC. The VRDC is a virtual research environment that allows researchers to have direct access to approved data files and be able to conduct their analysis within the CMS secure infrastructure. The VRDC contains its own VPN and virtual desktop. All reporting and/or publication of data will be in aggregate form. Additional protection of participant confidentiality mandated by HIPAA will be strictly adhered to.

All reporting and/or publication of data will be in aggregate form. Additional protection of participant confidentiality mandated by HIPAA will be strictly adhered to.

For the PRIM-ER Contextual Assessment and CDS quantitative survey and qualitative interviews the risks listed above will be managed and minimized by ensuring that only qualified study team members have access to patient data, unique identifiers are assigned to participant data, and all personal identifiers will be removed after final

analysis. The ZOOM teleconferencing interface will be an encrypted connection between the interviewer and interviewee. Participant information and data will be stored on REDCap software, which is an encrypted and secure data collection and storage system. This study will also adhere to, and exceed, federal, state, and institutional regulations regarding ethical conduct of research to protect subjects who choose to participate in this study. Interviews will be recorded and transcribed and confidentiality will be protected by immediately downloading the recording to a secure computer and deleting the recordings once they are transcribed. No identifiable information will be recorded. The interviews pose minimal risk to the participants.

Regarding the potential virtual trainings, NYULH's Zoom account will be used and the link, meeting ID and password will be distributed by each Site Principal Investigator to his/her staff members.

8. Data Collection, Safety, and Monitoring

A) Data Collection

We will estimate the baseline rate of acute care admission, healthcare utilization, and survival following the index ED visit using Medicare claims data for visitors to each ED. To evaluate the effect of PRIM-ER, we will use the Master Beneficiary Summary File, Inpatient, Outpatient, Home Health, and Hospice files to monitor acute care admission, healthcare utilization, and survival monthly for up to 6 months after the index ED visit to evaluate whether there is a change before and after implementation.

B) Provisions to Monitor Data and Ensure the Safety of Subjects

All study data will be stored and accessed via secure systems. Data will not be accessed or analyzed by individual sites; these activities will be performed exclusively by authorized individuals at the lead study site (NYU School of Medicine). Only authorized personnel who have been appropriately trained will be granted permission by the PI to access study data. A Data Safety Monitoring Plan (DSMP) will be submitted for reporting procedures of adverse events and serious adverse events.

C) Steering Committee

The PRIM-ER Steering Committee (SC) is the primary governing body of PRIM-ER. In consultation with the NIH Program Officer, NIH Scientific Officer, and NIH Collaboratory leadership, it formulates and monitors policies and procedures guiding the research activities. All major scientific and operational decisions are made by majority vote with the concurrence of the NIH Program Officer, NIH Scientific Officer, and NIH Collaboratory leadership. The Steering Committee may appoint Subcommittees and Working Groups as needed to carry out specific tasks identified by the Steering Committee. The Steering Committee will function in accordance with the Terms and Conditions of the NIH Collaboratory Demonstration Project RFA and other applicable policies of NIH, NIA, and NCCIH. All participating PRIM-ER sites must agree to abide by the policies approved by the Steering Committee.

The voting membership of the committee is to consist of the Principal Investigator, a site Principal Investigator from each of the other 17 health care systems, the NIH Program Officer, the NIH Scientific Officer, and leadership from the NIH Collaboratory as requested. Other (non-voting) memberships also include the Program Manager and other Subcommittee and Work Group Members.

This committee will establish bylaws, policies, and standard operating procedures to govern all aspects of PRIM-ER. This committee will review and approve the collaborative research agenda as well as formulate and monitor policies and procedures guiding the research activities, review and approve procedures for data acquisition, analysis and management, oversee communication within the PRIM-ER as well as with the greater scientific community and the public.

The Steering Committee will be responsible for ensuring that there are well documented policies and operating procedures guiding all aspects of PRIM-ER activities (e.g., protocol development, review, initiation, conduct, and closure, data collection, publication, etc.) and bylaws delineating the requirements and expectations of collaborating institutions, membership criteria, review of research progress and performance, establish standards of performance, and procedures for removing institutions due to poor performance.

The Steering Committee will establish subcommittees and workgroups to assist it in carrying out its functions. The Steering Committee may meet up to four times a year.

D) Data and Safety Monitoring Plan

The PI, in cooperation with her co-investigators, the DSMB, and the IRB at NYU School of Medicine, will monitor the safety of the implemented project. The project manager will inform the PI immediately of any adverse events (AEs) that meet the collection and reporting criteria of the Data Safety Monitoring Plan (DSMP). All serious adverse events (SAEs) and Unanticipated Problems (UPs) related to study participation will be reported to the IRB and the NIA according to the criteria outlined in the DSMP. Events that might be considered AEs related to this proposal include emotional distress resulting from discussions surrounding palliative care, and any breaches in subject confidentiality. Related AEs and related SAEs will also be reported annually in the IRB for continuation or termination of the research. Given the minimal risk entailed by this project for all participating populations, we do not anticipate the occurrence of many AEs or SAEs. The PI and co-investigators will be versed in these reporting procedures, as they are currently required for all research conducted at NYU School of Medicine. All investigators and staff involved in this project have completed an extensive course and passed a certifying exam on the protection of human subjects in research. Independent Monitors comprised of a researcher in palliative care, biostatistician, and palliative care physician and content expert will monitory the data safety of this study. The study team will generate Study Reports for the Independent Monitors and will provide information on the following study parameters:

- Demographic information pertaining to patient subjects obtained in Medicare Claims.
- Stopping and reporting rules for UPs and related AEs/SAEs. A summary report will be generated consisting of the number of related AEs and SAEs by site and in total and delineated by severity.
- Any protocol deviations that have occurred since the previous report.
- Quality management activities since the last review, including frequency. A summary of findings and corrective actions taken to address the findings will be included.
- Interim analyses as requested by the IMC to assess safety concerns or study futility.

Study Report tables will be generated only from aggregate (not by group assignment) baseline and aggregate safety data for the study population.

For the PRIM-ER Contextual Assessment and CDS quantitative survey, data collection, safety, and monitoring plan will adhere to, the data safety and monitoring plan outlined above for PRIM-ER grant, as applicable. For all the Semi-structures qualitative interviews confidentiality will be protected by immediately downloading the recording to a secure computer and deleting the recordings once they are transcribed. No identifiable information will be recorded. The interviews pose minimal risk to the participants.

9. Economic Impact to Subjects

There is no expected economic impact to subjects participating in this study.

10. Payments to Subjects

Patient participants will not receive compensation in this study.

11. Vulnerable Populations

Given the magnitude of the Medicare Claims Database, it is possible that adults unable to consent will be included. Since we are requesting a waiver of authorization, this should not pose any additional risk to these subjects.

Include	Exclude	Vulnerable Population Type
Х		Adults unable to consent
	Х	Individuals who are not yet adults (e.g., infants, children, teenagers
	Х	Wards of the State (e.g., foster children)
	Х	Pregnant women
	Х	Prisoners

REFERENCES

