An ED visit is often described as a sentinel event signifying a breakdown in care coordination for older adults.^{8,9} Since EDs sit at the crossroads of ambulatory and inpatient care, they can and often play a pivotal role in balancing the potential harms and benefits of hospitalization for seriously ill, vulnerable older adults.¹⁰⁻¹³ Hospitalization for older adults carries significant risks such as iatrogenic complications, functional and cognitive decline, and loss of independence¹⁴⁻¹⁹ but emergency providers may be unaware of safe alternatives.

Emergency medicine developed as a specialty to treat the acutely ill and injured, yet EDs increasingly care for older adults with multiple comorbid conditions who present for acute exacerbations of chronic illness. Visits to the ED by older adults are increasing both in frequency and as a proportion of all ED visits. In 2011, adults aged 65 years and older comprised 15% of total ED visits, had the highest severity of illness, and represented 44% of all admissions from the ED.²⁰ The number and rate of admissions to the Intensive Care Unit (ICU) by emergency providers have also increased, especially among older adults.²¹ The proportion of the US population 65 years and older will continue to grow, and EDs will see an increase in both the number of older adults and the complexity of care they are required to provide.²² The ED presents a key decision point at which providers set the subsequent care trajectory, including whether an older adult is hospitalized and to which setting. Emergency physicians can thus play an integral role in transforming care for older adults through evidence-based models of care delivery that emphasize tradeoffs between potential benefits and potential harms.²³ However, until recently, little attention has been paid to the delivery of goal-concordant care in the ED for older adults with serious illness. The default treatment plan is to deliver treatment intensive care that favor life-sustaining therapies, many of which may be contrary to what older adults desire.

3. Settings of the Human Research

The PRIM-ER quality improvement (QI) initiative will be implemented in the Emergency Departments at the following sites:

Site	Location
NYU School of Medicine	
Perelman Center for Emergency Care	New York, NY
Bellevue Hospital Center	New York, NY
NYU Langone Hospital – Brooklyn	Brooklyn, NY
NYU Long Island	Mineola, NY
Allegheny Health Network	
Allegheny General Hospital	Pittsburgh PA

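### One access score per health system hides differences between that system's EDs on the location-based items, and the plan gives no rule for combining several sites

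*Combined protocol and SAP*

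**What the plan says.** All references are to the combined protocol and SAP.

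- **Unit of the score.** Under Exploratory Analysis, in the study design description, "Each healthcare system will be assigned a score based on their access to home and community health services". The Contextual Assessment paragraphs of E) Data Analysis then state that "Each healthcare system index score will be used as an independent variable in our predictive model".
- **Level of the contextual data.** The same paragraphs say of the grey literature review: "Data will be collected and analyzed on the regional, state, and healthcare system level". No ED level is mentioned. The provider interviews recruit one physician and one nurse per system.
- **Content of the census.** Under Grey Literature Review, the environmental scan covers the "type, amount, and location of home and community health services relative to the location of the healthcare systems of interest", and the data of interest include "distance/location of facilities in relation to healthcare systems".
- **Geography.** Section 3 (Settings) lists four EDs under one system: two in New York, one in Brooklyn, and "NYU Long Island" in Mineola.
- **Outcome side.** C) Number of Subjects describes patients "who have made their index ED visit to any of the 35 EDs". Table 1 carries ED, coded 1 to 35, as a variable separate from health system. The exploratory analysis is to follow the parent utilization model. Section c (Methods) describes multilevel models with patients nested in hospitals and, for ED disposition, random effects at site level.

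The available text does not say which location represents a system with several EDs, or how their values are combined. It gives no power or sample size calculation for this analysis.

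**The concern.** The number of facilities nearby and the distance to them are local quantities. Each outcome follows a visit to one particular ED. For a system whose EDs lie in several towns, distance to services has no single value, so one score for the system must be either a blend or the value of one chosen place.

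In both cases the analysis cannot use differences in local access between EDs of the same system. Those comparisons hold system-wide policy fixed, so they help most in separating local availability from system practice. The stated question is whether access predicts utilization. A weak or null association would be harder to interpret if the exposure had been blurred or placed at the wrong location.

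**Working it through.** The plan has no figure of its own to reproduce here. The check is a count from stated numbers, a short derivation, and an illustrative simulation.

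**1. Contrasts lost (stated inputs: 35 EDs, 18 systems).**

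- Between-ED degrees of freedom: 35 − 1 = 34.
- Between-system degrees of freedom: 18 − 1 = 17.
- Within-system contrasts: 35 − 18 = 17, and 17/34 = 50%.

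A system score is constant on those 17 by construction. In the system listed with New York, Brooklyn and Mineola sites, four EDs share one value, so 4 − 1 = 3 contrasts are lost there.

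**2. Effect on the slope.** Let *x* be true access at an ED and *w* the share of its between-ED variance that lies within systems. The value of *w* is not in the documents.

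- *Score is the mean of the system's EDs.* The difference between *x* and the mean is uncorrelated with the mean (Berkson-type error). The slope is therefore unbiased and only precision falls.
- *Score is the value at one ED per system.* For the 18 chosen EDs the score equals *x*. For the other 17, the regression of *x* on the score has slope 1 − *w*. Averaged over 35 EDs, the attenuation factor is approximately [18 + 17(1 − *w*)]/35 = 1 − (17/35)*w*. At *w* = 0.25, 0.50 and 0.75 this gives 0.88, 0.76 and 0.64. A simulation with one set of assumed system sizes (one of 4, fourteen of 2, three of 1) gave 0.89, 0.76 and 0.64.

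**3. Effect on power.** All inputs here are assumptions: system sizes 4, 3, 3, 3, 3, 3, 2, 2, 2, 2 and eight of 1 (total 35 EDs in 18 systems); ED-level correlation 0.4; no further system effect on the outcome; linear regression of ED or system means; two-sided 5% test.

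| Share *w* | ED-level score | System average, weighted by number of EDs | System average, unweighted |
|---|---|---|---|
| 25% | about 67% | about 58% | about 50% |
| 50% | about 66% | about 51% | about 47% |
| 75% | about 67% | about 46% | about 43% |

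The weighted column is the fairer comparison, because a site-level model would not count a one-ED system as heavily as a four-ED system. At a 10% share the weighted figure is about 60 to 61%, against about 65% with ED-level scores. As *w* approaches zero the remaining gap is small and comes only from residual degrees of freedom (18 − 2 = 16 instead of 35 − 2 = 33).

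In the same runs the system-average slope was 0.40 at every share, equal to the true value. With one location standing for the system and *w* = 50%, it was 0.33 unweighted and 0.31 weighted.

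**The case against.** The strongest reply is that the system level is the plan's declared and consistent choice. The Contextual Assessment is framed around regional, state and health-system factors, its data are collected at those levels, and its interviews are one physician and one nurse per system. Laws, in-system services and interview responses either do not vary by ED or are not observed by ED, so for them a system score loses nothing. This stands. The point is limited to the location-based census items and is not an internal contradiction.

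Second, a reader might infer that the planned score biases the association toward zero. The documents do not support that as a general statement. No reference location or main campus is named, and under averaging the slope is unbiased. Attenuation follows only if one place stands for the system.

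Third, the within-system share and the system sizes are assumed. Only one system's multi-town spread can be relied on here, because part of the site table is not available for review. The documents as read cannot show how common such a spread is among the other systems.

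Fourth, the simulation treats access at the ED's location as error-free. Patients are community-dwelling and may live some distance away, so the 67% benchmark is optimistic.

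These replies limit the size of the point. They do not restore the 17 contrasts or supply the missing aggregation rule.

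**Conclusion.** The concern holds as a measurement-level weakness in an exploratory analysis. Two parts rest on the documents alone: the score is constant on 17 of 34 between-ED contrasts, and no rule says how a multi-ED system's location-based items are combined.

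The consequence is conditional. Averaging costs precision only: about 9, 15 and 21 percentage points of power (67 − 58, 66 − 51, 67 − 46) at assumed shares of 25, 50 and 75%, and little near zero. A single reference location would also shrink the slope, to about three quarters of its true value at a 50% share. These sizes are illustrations under the stated assumptions, not estimates for this trial.

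A reader might also infer that the trial's main results are affected. They are not: the score enters only the exploratory Contextual Assessment, and the primary and secondary analyses do not use it. This is a worthwhile low-cost improvement, not an error that threatens the trial.

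**What to change.** - Compute the census items (counts of services and distances to them) at each of the 35 ED locations.
- Keep state regulation, in-system services and interview-based items at their own level and attach them to each ED.
- Use the resulting ED-level score as the independent variable in the predictive model, with a system-level random effect added to the site-level one. Some components will still be shared by all EDs of a system, and site effects alone would treat those EDs as independent.
- If a single system score is kept, state the aggregation rule and note that within-system differences in local access are not examined.

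The cost is extra abstraction: 35 locations instead of 18, so 17 more, using the same sources. Interview items stay at system level. ED location also remains only a proxy for where patients live, and the report should say so.
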